## 7 STUDY OBJECTIVES AND ENDPOINTS

### 7.1 Primary objective and endpoints

**Table 7.1-1 Primary objective and endpoints**

Primary objective	Primary endpoints	Assessment
To evaluate and compare $C_{max}$ and $AUC_t$ of nicotine after the use of each product.	$C_{max}$ and $AUC_t$	PK sampling and analysis, see Section 11.3.1

### 7.2 Secondary objectives and endpoints

**Table 7.2-1 Secondary objectives and endpoints**

Secondary objectives	Secondary endpoints	Assessment(s)
To evaluate other PK parameters of nicotine after the use of each product	
 
• <math>AUC_{0-90}</math>
 
• <math>AUC_{inf}</math>
 
• time to <math>C_{max}</math> (<math>T_{max}</math>)
 
• plasma concentration at last timepoint measured (<math>C_{last}</math>)
 
• terminal elimination half-life (<math>T_{1/2}</math>)
 
	PK sampling and analysis, see Section 11.3.1
To evaluate orally extracted dose of nicotine in used products (OND)	The orally extracted dose of nicotine from each pouch will be calculated to evaluate the correlation between baseline-adjusted $AUC_{inf}$ and orally extracted dose of nicotine.	Collection and analysis of pouches, see Section 11.4.2
To evaluate product perception and preference by use of subjective assessments	Subjective assessment endpoints including: PES, PPS and the Urge to use questionnaire	PES, see Section 11.4.3 PPS, see Section 11.4.4 Urge to use questionnaire, see Section 11.4.5
To evaluate the tolerability and safety of each of the products used	
Frequency, intensity and seriousness of AEs
 
Clinically significant changes in laboratory parameters, vital signs and ECG
	AE reporting and questioning, see Section 11.4.6  Blood sampling for clinical chemistry and haematology, see Section 11.4.7 Blood pressure and pulse, see Section 11.4.8 12-lead ECG, see Section 11.4.9

## 8 STUDY DESIGN

### 8.1 Overall study design and schedule of events

This will be a randomised cross-over, single-blind, confinement study conducted in 27 male or female snus or nicotine pouch users. The study will investigate 4 different nicotine containing products in a cross-over design, incorporating PK evaluation, nicotine extraction evaluation, subjective questionnaire assessments as well as safety and tolerability evaluation.

During the study participation, subjects will come for 2 visits to the clinic, including a screening visit and a 4-day confinement period. A final follow up end-of-study telephone call will be performed within a week of last product use.

#### Visit 1 (Screening)

Visit 1 will take place from Day -28 to Day -1 and will include an eligibility check, review of health status and assessment of snus and nicotine pouch user habits, see Table 8.1-1 for details.

Subjects will be advised of the risks of using nicotine and referred to nicotine-use cessation support to quit if that is their intention.

#### Visit 2 (In-clinic treatment period, Day -1 to Day 4)

At Visit 2, subjects will be admitted to the clinic on Day -1 and will remain at the clinic until Day 4 for daily single IP use and PK blood sampling, nicotine extraction, subjective questionnaire assessments and safety assessments.

On Day -1, baseline vital signs, ECG and clinical laboratory profile assessments will be performed. Subjects are allowed to use their own snus or nicotine pouch product until 10 pm of Day -1. On Day -1 the subjects will also undertake a familiarisation session of the study products and questionnaires. The clinical team will explain how the products will be used and the subjects will have the opportunity to see the product and packaging. An explanation of how the questionnaires will be distributed to the subjects will be given. The familiarisation session does not include a product trial and the products used in the session will not be used in the clinical study but will be retained as demonstration samples for accountability purposes.

In the morning of Day 1, after pre-use assessments and confirmation of eligibility, the subjects will be randomised and then administered a single pouch of the IP in the sequence to which they have been randomised. Oral nicotine IP will be used for 20 minutes according to standard use instructions. PK sampling will be done pre-IP use and at 5, 10, 15, 20, 25, 30, 45, 60, 90 minutes, 2, 4, 6 and 8 hours post start of IP use. Used pouches will be collected for analysis of nicotine extraction. Questionnaires will be distributed to the subject at defined intervals throughout the day. Safety will be followed throughout the day. Subjects will be allowed to use their own nicotine containing products *ad lib* after the 8-hour timepoint until 10 pm.

In the morning of Day 2, after pre-IP use assessments, the subjects will be administered a single pouch of the IP in the sequence to which they have been randomised. IP will be used for 20 minutes according to standard use instructions. PK sampling will be done pre-IP use and at 5, 10, 15, 20, 25, 30, 45, 60, 90 minutes, 2, 4, 6 and 8 hours post start of IP use. Used pouches will be collected for analysis of nicotine extraction. Questionnaires will be distributed to the subject at defined intervals throughout the day. Safety will be followed

throughout the day. Subjects will be allowed to use their own nicotine containing products *ad lib* after the 8-hour timepoint until 10 pm.

In the morning of Day 3, after pre-IP use assessments, the subjects will be administered a single pouch of the IP in the sequence to which they have been randomised. IP will be used for 20 minutes according to standard use instructions. PK sampling will be done pre-IP use and at 5, 10, 15, 20, 25, 30, 45, 60, 90 minutes, 2, 4, 6 and 8 hours post start of IP use. Used pouches will be collected for analysis of nicotine extraction. Questionnaires will be distributed to the subject at defined intervals throughout the day. Safety will be followed throughout the day. Subjects will be allowed to use their own nicotine containing products *ad lib* after the 8-hour timepoint until 10 pm.

In the morning of Day 4, after pre-IP use assessments, the subjects will be administered a single pouch of the IP in the sequence to which they have been randomised. IP will be used for 20 minutes according to standard use instructions. PK sampling will be done pre-IP use and at 5, 10, 15, 20, 25, 30, 45, 60, 90 minutes, 2, 4, 6 and 8 hours post start of IP use. Used pouches will be collected for analysis of nicotine extraction. Questionnaires will be administered to the subject at defined intervals throughout the day. Safety will be followed throughout the day. Subjects will leave the research clinic after completing all 8 h-assessments on Day 4.

[figure not shown]
#### Visit 3 (End-of-Study phone call)

A follow-up telephone call (Visit 3, end-of-study) will be made on Day 7 ( $\pm 1$ ) to follow-up on any AEs.

Subjects will participate in the study for up to 35 days, including an up to 28-day screening period.

An overview of the study design is shown in Figure 8.1-1.

**Figure 8.1-1 Overview of study design**

The schedule of events for the study is shown overall in Table 8.1-1 and detailed for Days 1 to 4 in Table 8.1-2. Study assessments are described in Section 11.

**Table 8.1-1 Overall schedule of events**

Visit	Refer to CSP section:	Screening	In-Clinic					End-of-study
		Visit 1	Visit 2					Visit 3 Phone call
Assessment		Day -28 to Day -1	Day -1	Day 1	Day 2	Day 3	Day 4	Day 7 (+/- 1 day)
Informed Consent	14.3	X						
Inclusion/exclusion criteria	9.4, 9.5	X	X 	X 				
Demographics	11.2.3	X						
Nicotine-use habits	11.2.14	X						
Medical/surgical history	11.2.6	X						
HIV, hepatitis B and C	11.2.8	X						
Alcohol test	11.2.12	X	X					
Urine Drug Screen	11.2.11	X	X					
Pregnancy Test (WOCBP only)	11.2.10	X 	X 					
Weight/height (BMI)	11.2.5	X						
Physical Examination	11.2.4	X						
Clinical Laboratory Profile	11.4.7	X	X				X	
Vital Signs (Blood pressure and pulse)	11.4.8	X	X	X	X	X	X	
12-lead ECG	11.4.9	X	X				X	
PES	11.4.3			X	X	X	X	
PPS	11.4.4						X	
Urge to use questionnaire	11.4.5			X	X	X	X	
Randomisation	9.9			X				
IP use	10.6			X	X	X	X	
PK blood sampling	11.3.1			X	X	X	X	
Nicotine pouch collection	11.4.2			X	X	X	X	
Meals 	9.6.1		X	X	X	X	X	
Baseline symptoms 	11.2.13	X	X	X				
Adverse events 	11.4.6				----- X -----			
Prior and concomitant medications	11.2.7			----- X -----				

BMI = Body mass index, CSP=clinical study protocol, WOCBP = women of childbearing potential, HIV = human immunodeficiency virus

1. Confirmation of eligibility criteria on Day-1 or Day 1
2. WOCBP only. Urine dipstick.
3. Meals (breakfast, lunch, snack, dinner and evening snack) will be served at the research clinic during Visit 2. On Days 1 to 4, lunch, snack, dinner and evening snack will be served approximately 4, 7, 9 and 11 hours, respectively, after start of each IP use. Breakfast will be served approximately 1 hour before start of each IP use.
4. Baseline symptoms will be recorded up until start of first use of IP on Day 1.
5. Adverse events will be recorded from start of first use of IP on Day 1

Table 8.1-2 Detailed schedule of events for Day 1, Day 2, Day 3 and Day 4 (Visit 2)

Assessment /time-point	Pre-IP use	Day 1, Day 2, Day 3 and Day 4														
		00:00	00:05	00:10	00:15	00:20	00:25	00:30	00:45	01:00	01:30	02:00	04:00	06:00	08:00	
Inclusion/exclusion criteria	X 															
Vital signs (Blood pressure and pulse)	X															X
12-lead ECG																X 
Clinical laboratory profile																X 
PES questionnaire																X
PPS questionnaire																X 
Urge to use questionnaire	X		X	X	X	X	X	X	X	X	X	X	X	X	X	X
Randomisation	X															
IP use						X										Ad lib use until 10 pm 
PK blood sampling 	X		X	X	X	X	X	X	X	X	X	X	X	X	X	X
Nicotine pouch collection							X									
Meals 																
Baseline symptoms 	X															
Adverse events 												X				
Prior and concomitant medications													X			

1. Confirmation of eligibility criteria on Day-1 or Day 1.
2. Day 4 only (i.e. not on Days 1 to 3).
3. Subjects will be allowed to use their own nicotine products after the 8 hour PK sample until 10 pm each day.
4. PK sampling for 8 hours post-IP use on Days 1 to 4. Pre-use sample to be taken within 5 minutes of start of IP-use. PK sampling time windows, refer to Section 11.3.1.
5. Meals (breakfast, lunch, snack, dinner and evening snack) will be served at the research clinic during Visit 2. Lunch, snack, dinner and evening snack will be served approximately 4, 7, 9 and 11 hours, respectively, after start of each IP use. Breakfast will be served approximately 1 hour before start of each IP use.
6. Baseline symptoms will be recorded up until start of first use of IP on Day 1.
7. Adverse events will be recorded from start of first use of IP on Day 1.

## 8.2 Rationale for study design

The study will provide important PK, safety and tolerability data to support the design of further studies. The time points for PK blood sampling were selected based on data obtained from previous non-clinical and clinical studies.

A crossover design was chosen to yield a more efficient comparison of treatments than a parallel study design, i.e., fewer subjects are required since each subject will serve as its own control.

Randomisation will be used to minimise bias in the assignment of subjects to a treatment sequence.

The study will be single-blind, i.e. the subjects will not know the identity, and most importantly, not the strength/nicotine content of each IP. A single-blind approach will reduce potential bias during data collection, in particular during the collection of questionnaire data, and evaluation of endpoints.

## 9 STUDY POPULATION

Prospective approval of protocol deviations to eligibility criteria, also known as protocol waivers or exemptions, is not permitted.

### 9.1 Recruitment

The subjects will be recruited from CTC's database of healthy volunteers and from advertising in media (including social media).

### 9.2 Screening and enrolment log

Investigators must keep a record of all screened subjects even if they were not subsequently included in the study. This information is necessary to verify that subjects were selected without bias. The reason for screen failure should be stated for all subjects screened but not included. The reason for withdrawal should be stated for all subjects included but not completed.

A screening number will be allocated to each subject in connection to the informed consent process at the Screening visit. The screening number is generated automatically in the electronic case report Form (eCRF). The screening number will allow identification of subjects irrespective of their possible eligibility for the study.

Subjects included and randomised will be assigned a randomisation number (101, 102 etc.).

If a subject cannot perform the first planned use of IP within 28 days after screening (*i.e.*, the time interval between signing informed consent until first IP use) the subject should be rescreened before proceeding in the study.

### 9.3 Number of subjects

Approximately 54 subjects will be screened to achieve a total of 27 randomised subjects.

For replacements of subjects who discontinue from the study, see Section 9.8.

#### 9.4 Inclusion criteria

For inclusion in the study, subjects must fulfil the following criteria:

1. Willing and able to give written informed consent for participation in the study.
2. Male or female subject aged  $\geq 19$  years at the time of screening.
3.  $\text{BMI} \geq 18.0$  and  $\leq 30.0 \text{ kg/m}^2$ .
4. Clinically normal medical history, physical findings, vital signs, ECG and laboratory values at the time of screening, as judged by the Investigator.
5. User of snus or nicotine pouches for  $\geq 1$  year, with a minimum weekly use of 2 or more snus or nicotine pouch cans and who is willing and considered able to use brands with nicotine content in the range of 14 to 20 mg nicotine/pouch.

#### 9.5 Exclusion criteria

Subjects must not enter the study if any of the following exclusion criteria are fulfilled:

1. History of any clinically significant disease or disorder which, in the opinion of the Investigator, may either put the subject at risk because of participation in the study, or influence the results or the subject's ability to participate in the study.
2. Any clinically significant illness, medical/surgical procedure or trauma within 4 weeks of the first use of IP.
3. Any planned major surgery within the duration of the study.
4. Any positive result on screening for serum hepatitis B surface antigen, hepatitis C antibody and HIV.
5. After 10 minutes supine rest at the time of screening, any vital signs values outside the following ranges:
  - Systolic blood pressure  $<90$  or  $>140 \text{ mmHg}$ , or
  - Diastolic blood pressure  $<50$  or  $>90 \text{ mmHg}$ , or
  - Pulse  $<40$  or  $>90 \text{ bpm}$
6. Female subjects who are pregnant, who are currently breast feeding or who has the intent to become pregnant.
7. History of severe allergy/hypersensitivity or ongoing allergy/hypersensitivity, as judged by the Investigator, or history of hypersensitivity to drugs with a similar chemical structure or class to nicotine.
8. Planned treatment or treatment with another IP within 1 month or investigational drug within 3 months prior to Day -1. Subjects consented and screened but not dosed in previous phase I studies are not excluded.
9. Positive screen for drugs of abuse or alcohol at screening or on admission to the research unit prior to use of the IP.
10. History of alcohol abuse or excessive intake of alcohol, as judged by the Investigator.

11. Presence or history of drug abuse, as judged by the Investigator.
12. History of, or current use of, anabolic steroids, as judged by the Investigator.
13. Excessive caffeine consumption defined by a daily intake of >5 cups of caffeine containing beverages.
14. Plasma donation within one month of screening or blood donation (or corresponding blood loss) during the three months prior to screening.
15. Subjects who intend to change their nicotine-use habit or make a quit attempt within the next 3 months from the screening visit.
16. Investigator considers the subject unlikely to comply with study procedures, restrictions and requirements.

## 9.6 Restrictions during the study

The subjects must be willing to comply to the following restrictions during the entire study duration *i.e.*, from screening to the end-of-study visit.

### 9.6.1 **General restrictions**

- Subjects shall abstain from snus and all other nicotine containing products from 10 pm the evening prior to the anticipated start of each IP use on Days 1 to 4.
- Use of other nicotine-containing products, than defined by this study protocol, is not allowed during the study from 10 pm Day-1 until the end of Visit 2.
- Subjects are not allowed to eat or drink or conduct any other mouth related procedure (e.g. tooth brushing) 30 minutes before IP use, during IP use and 30 minutes after the IP has been taken out.
- Meals and Dietary Restrictions:

Meals will be served while the study subjects are in the research clinic. Breakfast will be served approximately 1 hour prior to IP use. Lunch will be served 4 hours after start of each IP use. Snack, dinner and evening snack will be served approximately 7, 9 and 11 hours post-IP use, respectively. Water is allowed *ad lib* at the clinic except 30 minutes before IP use until 30 minutes after IP use on Days 1 to 4.

- Alcohol: Consumption of alcohol is not allowed within 48 hours prior to the screening visit or Visit 2. Consumption of alcohol is not allowed during the subject's stay at the clinic during Visit 2.
- Drugs of abuse: Use of drugs of abuse is not allowed during the study. In addition to the urine drug testing described in Table 8.1-1, additional random testing can be performed at the clinic visits.
- Coffee: Not more than 5 cups of coffee per day will be allowed from admission to the clinic on Day -1 until the end of Visit 2.
- Xanthine or taurine containing products/beverages: Energy drinks (e.g. Red bull) are not allowed from admission to the clinic on Day -1 until the end of Visit 2.
- Exercise: The subjects must refrain from strenuous exercise (defined as greater than 70% of the maximal pulse rate for one hour or more) during Visit 2.

- Blood donation: The subjects must not donate blood or plasma during the study until 3 months after the end of Visit 2.
- Participation in other clinical studies: Study subjects are not allowed to participate in any other interventional clinical study during the study period.
- Visits to the clinic: Subjects are not allowed to leave the research clinic during study visits, unless authorised by the study personnel.

### 9.6.2 ***Prior and concomitant therapy***

Medications (prescribed or non-prescribed medication including antacids, analgesics, herbal remedies, vitamin supplements and minerals) considered necessary for the subject's safety and wellbeing may be given at the discretion of the Investigator during the residential period. Following consultation with the Sponsor, the Investigator will determine whether or not the subject should continue in the study.

## 9.7 **Screen failures**

Screen failures are defined as subjects who consent to participate in the clinical study but do not fulfil all eligibility criteria and are not subsequently randomised in the study. A minimal set of screen failure information is required to ensure transparent reporting of screen failure subjects. Minimal information includes documentation of signed and dated informed consent form (ICF) and reason(s) for screening failure.

Subjects who do not meet the criteria for participation in this study may be rescreened.

Re-screening can be performed if any of the following were reasons for screening failure or non-randomisation (as judged by the Investigator):

- Practical reasons.
- Non-significant medical conditions (e.g. influenza, nasopharyngitis).
- Reserve subject in a previous group
- Plasma or blood donation outside allowed time windows.

For subjects who are re-screened, a new screening number will be assigned and a new, signed ICF will be collected.

## 9.8 **Subject withdrawal**

### 9.8.1 ***General withdrawal criteria***

Subjects are free to discontinue their participation in the study at any time and for whatever reason without affecting their right to an appropriate follow-up investigation or their future care. If possible, the reason for withdrawal of consent should be documented.

Subjects may be discontinued from the study at any time at the discretion of the Investigator.

Reasons for discontinuation include:

- Subject decision
- Severe non-compliance to study protocol procedures, as judged by the Investigator and/or Sponsor

- Subject is lost to follow-up.
- Significant AEs posing a risk for the subject, as judged by the Investigator and/or Sponsor
- Withdrawal of informed consent to the use of biological samples
- Pregnancy
- Death
- Meeting of an exclusion criterion during the study, which, in the opinion of the Investigator, may pose a risk for the subject

#### 9.8.2 *Procedures for discontinuation of a subject from the study*

A subject who prematurely discontinues participation in the study will always be asked about the reason(s) for discontinuation and the presence of any AEs. If a subject withdraws consent, the Investigator must ask the subject if he/she is willing, as soon as possible, to be assessed according to the procedures scheduled for the end-of-study visit. Any ongoing AEs will be followed as described in Section 11.4.6.12.

The primary reason for discontinuation/early withdrawal must be specified in the eCRF and final product accountability must be performed.

#### 9.8.3 *Subject replacement*

Subjects who are prematurely withdrawn from the study for any reason may be replaced during the course of the study.

### 9.9 Randomisation

On Day 1, subjects will be randomised to one of 4 treatment sequences. The 4 different products are:

- **A:** ZoneX #5 slim 14 mg nicotine/pouch
- **B:** ZoneX #5 16 mg nicotine/pouch
- **C:** ZoneX #6 20 mg nicotine/pouch
- **D:** Skruf Slim Fresh #5 16.6 mg nicotine/ pouch

The 4 randomisation sequences are:

- **Sequence 1:** A:B:C:D
- **Sequence 2:** B:C:D:A
- **Sequence 3:** C:D:A:B
- **Sequence 4:** D:A:B:C

A computer-generated randomisation list will be created by CTC using SAS Proc Plan, SAS Version 9.4 (or later). The randomisation list will contain subject number, sequence and treatment and will be kept by the randomiser until database lock. A copy of the randomisation list will be provided to the research clinic.

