## 10.6 Treatment administration

In the morning of Days 1 to 4, subjects will be administered a single pouch as randomised.

Following completion of the single use session and after the 8-hour PK sample, the subjects will be allowed to use their own nicotine containing products *ad lib* after the 8-hour timepoint until 10 pm each day.

All IPs will be used in the same way as follows:

- A pouch of IP will be placed between the upper lip and gum and will be kept still there for 20 minutes.
- The IPs, being oral nicotine pouches, should not be chewed during use.
- The IPs should not be swallowed (swallowing saliva during IP use is allowed).

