### 17.2 Determination of sample size

No formal sample size calculation has been performed for this study. The proposed sample size is considered sufficient to provide adequate information for the study objectives.

Approximately 54 subjects will be screened to achieve 27 randomised subjects.

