Log transformed nicotine  $C_{max}$  and  $AUC_t$  estimates will be evaluated separately in a linear mixed-effects analysis of variance model with fixed effects for period, sequence, and product, and a random effect for subject. If the assumptions for this model will be inappropriate will the fixed effects period and sequence be removed from the model. The above product differences will be back-transformed to present the ratios of geometric least squares (LS) means and 95% CIs of each test product versus each other from the same model.

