4.5 Randomisation

On Day 1, subjects will be randomised to one of 4 treatment sequences. The 4 different products are:

- A: ZoneX [REDACTED] nicotine/pouch
- B: ZoneX [REDACTED] nicotine/pouch
- C: ZoneX [REDACTED] nicotine/pouch
- D: [REDACTED] nicotine/ pouch (comparator product)

The 4 randomisation sequences are described in the table below:

Sequence	Order			
Sequence 1	A	B	C	D
Sequence 2	B	C	D	A
Sequence 3	C	D	A	B
Sequence 4	D	A	B	C

A computer-generated randomisation list will be created by CTC using SAS Proc Plan, SAS Version 9.4 (or later). The randomisation list will contain subject number, sequence and treatment and will be kept by the randomiser until database lock. A copy of the randomization list will be provided to the research clinic.

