9.2 Changes of fixed effects for primary analysis

In the protocol (Synopsis and Section 17.5) it was stated that the linear mixed-effects model for the primary analysis should include fixed effects for period, sequence, and product, and a random effect for subject. The fixed effects for period and sequence will be removed for the statistical analysis. The subjects will be allowed to use their own nicotine containing products ad lib after the 8-hour timepoint until 10 pm. Hence, keeping period and sequence in the model adds no extra value to the analysis.

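### The cyclic sequences leave carry-over almost completely confounded with product; a Williams square of the same size would cut that exposure to a third

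*Protocol*

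**What the plan says.** Protocol 9.9: "On Day 1, subjects will be randomised to one of 4 treatment sequences". It lists A:B:C:D, B:C:D:A, C:D:A:B and D:A:B:C. SAP 4.5 repeats them ("The 4 randomisation sequences are described in the table below"), and SAP table shells 14.1.1, 14.1.2 and 14.1.4 are laid out by sequence.

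The periods are consecutive days (Protocol 10.6): "In the morning of Days 1 to 4, subjects will be administered a single pouch as randomised". Own products may be used after the 8-hour sample until 10 pm. Under Protocol 9.6.1 subjects must "abstain from snus and all other nicotine containing products from 10 pm the evening prior to the anticipated start of each IP use".

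Protocol 17.5.1 plans a "linear mixed-effects analysis of variance model with fixed effects for period, sequence, and product, and a random effect for subject". SAP 8.1.1 keeps only product and random subject. SAP 9.2 points to the ad lib own-product use and concludes: "Hence, keeping period and sequence in the model adds no extra value to the analysis". Neither model has a carry-over term. Protocol 8.2, the design rationale, gives no carry-over assumption and no washout justification.

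SAP 4.3.1 makes D the reference in all three primary comparisons. The planned size is 27 randomised subjects (Protocol 9.3), and Protocol 17.2 says "No formal sample size calculation has been performed for this study".

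**The concern.** In a cyclic square the predecessor of a product is fixed. Whenever it is not used first, B follows A, C follows B, D follows C and A follows D. An effect of yesterday's product on today's measurement is therefore loaded onto one particular product instead of being spread over all of them. The reference D takes its whole load from C, the product with the highest stated nicotine content, and D enters every primary contrast.

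Two routes are plausible here. A PES rating may be made partly in contrast with the product used the day before. The day's product may also change how much own product is used that evening, and so shift the next morning's pre-use nicotine or urge. At stake are the PES tests against D and, to a lesser degree, the Cmax and AUCt ratios. The design also leaves little means of checking whether either effect is present.

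**Working it through.** **Inputs.** Sequences from Protocol 9.9 and SAP 4.5; models from Protocol 17.5.1 and SAP 8.1.1; N = 27 from Protocol 9.3. Since 27/4 = 6.75, 7/7/7/6 is taken as the split, with DABC the short sequence (an assumption). The documents give no carry-over figure to reproduce.

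**Step 1: predecessor pairs.** Four sequences give 4 × 3 = 12 adjacent pairs. Cyclic: AB, BC, CD and DA three times each, and the other eight ordered pairs never. ADBC, BACD, CBDA, DCAB: all 12 ordered pairs once, with each product once in each period.

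**Step 2: bias when carry-over is not modelled.** Let λ_X be the carry-over from product X, on the log scale for PK. With equal sequence sizes each product is used first in one of four sequences.
- Cyclic: the mean for A contains 0.75 λ_D, for B 0.75 λ_A, for C 0.75 λ_B and for D 0.75 λ_C.
- So A−D is biased by 0.75(λ_D − λ_C), B−D by 0.75(λ_A − λ_C) and C−D by 0.75(λ_B − λ_C).
- Williams: the mean for A contains 0.25(λ_B + λ_C + λ_D) and for D 0.25(λ_A + λ_B + λ_C), so A−D is biased by 0.25(λ_D − λ_A). B−D and C−D behave in the same way.

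The balanced coefficients are the same with or without period in the model. At 7/7/7/6 under the SAP model, A, B and C have a predecessor in 20/27 = 0.741 of uses and D in 21/27 = 0.778.

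**Step 3: cost of adjusting for carry-over.** In Periods 2 to 4 of the cyclic square only the sums τ_B + λ_A, τ_C + λ_B, τ_D + λ_C and τ_A + λ_D are observed (τ is the product effect). Only Period 1, which has no predecessor, separates the two parts. Least squares with subject, period, product and first-order carry-over gives the variance of a product contrast, in units of the within-subject variance σ²:

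| Design | No carry-over term | With carry-over term | Ratio |
|---|---|---|---|
| Cyclic, one subject per sequence | 0.50 | 2.75 | 5.5 |
| Williams, one subject per sequence | 0.50 | 0.55 | 1.1 |
| Cyclic, 7/7/7/6 | 0.0742 | 0.394 to 0.425 | 5.3 to 5.7 |
| Williams, 7/7/7/6 | 0.0742 | 0.081 to 0.083 | about 1.1 |

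Efficiency is 0.50/2.75 = 18% for the cyclic square and 0.50/0.55 = 91% for the Williams square. Without a carry-over term the two are equally precise.

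**Step 4: how large PK carry-over could be.** The documents give no half-life. For an assumed 1 to 4 h, the study nicotine left after 24 h is 0.5^(24/1), under 0.00001%, to 0.5^(24/4) = 1.6%. For own product last used at 10 pm, with an assumed 10 h gap, it is 0.5^(10/1) = 0.1% to 0.5^(10/4) = 18%. Evening own-product use is thus the larger source of residual nicotine.

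**Step 5: size on the ratio scale (assumed range only).** If λ_C exceeded λ_D by 2%, 5% or 10%, the cyclic A/D ratio would be multiplied by 1.02^−0.75 = 0.985, 1.05^−0.75 = 0.964 or 1.10^−0.75 = 0.931. Differences of the same size entering at 0.25 give 0.995, 0.988 and 0.976.

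**The case against.** The strongest reply is that the primary endpoints are pharmacokinetic and well separated in time. There is about a day between products, abstinence from 10 pm, and a pre-use sample in every period. SAP 6 calculates baseline-adjusted parameters when that sample is above the quantification limit, which targets residual nicotine directly. This largely stands for direct carry-over. It is incomplete for the evening-use route: the adjustment needs an estimable terminal rate constant, and SAP 8.1.1 mentions baseline-adjusted Cmax and AUCt for descriptive summary without saying clearly which version enters the model.

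Several stronger readings should be resisted:
- A reader might infer that carry-over and product cannot be separated at all. That is true only within Periods 2 to 4; over all four periods every product contrast is estimable, though poorly.
- A reader might infer that a Williams square removes the bias. Without a carry-over term a quarter of a carry-over difference still enters each contrast, and λ_D would still appear in all three contrasts with D because D is the shared reference.
- A reader might take the 2% to 10% range as expected. Nothing in the documents supports any particular value.
- A reader might apply 0.75 to the PPS. It does not carry over to a single ranking made after Day 4.

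The subjective exposure is also narrower than it may look. SAP 9.3 makes urge to use descriptive, although shell 14.2.5 still shows comparisons. PES is the subjective endpoint with clearly planned tests against D, and it is secondary. For those rank tests the predecessor pattern is the same, but 0.75 describes a difference in means.

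Finally, SAP 9.2 is a separate matter: restoring period and sequence leaves the balanced coefficient at 0.75.

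**Conclusion.** The point holds as an avoidable design weakness. First-order carry-over is almost completely confounded with product: about 18% efficiency if it is modelled, and 0.75 of a carry-over difference in each contrast with D if it is not, as planned. A Williams square of the same size brings these to about 91% and 0.25, with no loss of direct-contrast precision.

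No material bias in the Cmax or AUCt ratios has been shown, and the documents do not support claiming one. The practical exposure lies in the PES comparisons and in behavioural carry-over through evening own-product use. The coefficients assume first-order additive carry-over and equal sequence sizes; a 7/7/7/6 split changes them only slightly.

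**What to change.** **If the randomisation list is not yet in use:** replace the four sequences with a Williams square, for example ADBC, BACD, CBDA, DCAB, in Protocol 9.9, SAP 4.5 and SAP shells 14.1.1, 14.1.2 and 14.1.4. The numbers of sequences, subjects and visits stay the same. The cost is a new list and a numbered protocol amendment, which under Protocol 14.5 needs ethics approval if substantial.

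**If randomisation has begun:** keep the sequences. Tabulate pre-use nicotine and pre-use urge by preceding product, and add a sensitivity analysis of the product contrasts using Period 1 only. With 6 or 7 subjects per product that analysis compares different subjects and will be imprecise, so it can support the main result but not replace it. It needs no new data.

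The documents do not say which case applies. The study was planned from Q3 2021 and the SAP is dated 23 November 2021, so this must be established first.
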